## **4. STUDY DESIGN**

### **4.1. Study Description**

This will be a prospective, randomized, double-blinded placebo controlled, crossover trial. Following recruitment and informed consent, each participant will undergo three study visits, including baseline testing (visit 1), followed by two sets of exercise and vascular function tests (visit 2 and visit 3) at CCHMC. Twenty-six patients will be enrolled in this study.

### **4.2. Study Duration**

The total duration of this study is approximately 24 months. Enrollment is expected to take approximately 18 months. Data cleaning and analysis are expected to take approximately 6 months.

Each participant will be in this study for up to 6 weeks from their initial study visit. Pending availability, participants will complete all three study visits in a 4-6 week period.

## **5. SELECTION AND RECRUITMENT OF PARTICIPANTS**

The Fontan database at CCHMC will be used to screen for this study. Patients meeting eligibility criteria will be approached for participation during a regularly scheduled clinic visit at CCHMC. Alternatively, a letter of introduction approved by the IRB will be mailed to potential participants. In the letter, patients will be given the opportunity to opt-out of the study by calling the study line within one week of receiving the letter. After ten days, study personnel will call patients to further explain the study. If there is interest in the study, study personnel will mail a copy of the consent form and call the patients back so that they can further discuss the study. If the patient's interest continues, study personnel will schedule a research visit for the patient. Written consent as outlined in section 6.1 will be obtained at their next clinic or study visit prior to any study procedures being conducted.

### **5.1. Inclusion Criteria**

Subjects who meet all of the following criteria will be eligible for the study:

1. Patients age 18 years and older; and
2. Single ventricle patients status post Fontan procedure.

### **5.2. Exclusion Criteria**

Subjects who meet any of the following criteria will be excluded from the study:

1. Clinically unstable: these are patients who are experiencing new cardiovascular symptoms such as worsening shortness of breath, new onset arrhythmia, uncontrolled heart failure, or evidence of clinically significant cirrhosis or renal failure.
2. Evidence of Fontan pathway or intra cardiac obstruction as identified on prior clinically indicated imaging studies (echocardiography and MRI);
3. Evidence of left or right systemic ventricular systolic dysfunction with an EF of <40% on either ECHO or MRI from previously documented clinical data;
4. Presence of uncontrolled arrhythmias;
5. Unable to perform exercise testing for any reason or if deemed by the PI or designee that exercise testing would not be in the best interest of the participant
6. Currently pregnant and/or breastfeeding
7. Patient unable to provide informed consent
8. BMI > 35 mg/m^2
9. Currently taking sildenafil, tadalafil, udenafil

## **6. STUDY PROCEDURES**

All study procedures will occur at Cincinnati Children's Hospital Medical Center (CCHMC) main campus. The Heart Institute (HI) at CCHMC has an adult heart clinic where patients may be seen as well. The HI adult clinic is on site at the main hospital campus and therefore has full access to emergency medical staff onsite at the hospital. Participants will be asked to fast for 8-12 hours prior to each study visit. Participants taking vasodilators (ACE inhibitors, angiotensin receptor blockers) will be asked to not take their medication on the day of the study for each visit, but can continue to take vasodilators in between visits. Participants will receive a light meal at the visits after completing the part of assessments that require fasting.

The following procedures will occur during the study:

### Baseline visit (Visit 1)

- Informed Consent
- Review of Demographics, Medical history, and Medications
- Urine pregnancy testing (for females of childbearing potential)
- Baseline vitals (heart rate, blood pressure, oxygen saturation, height and weight)
- Maximal cardiopulmonary exercise testing/Ramp protocol (including spirometry).
- Venous structure and function testing
- Light meal and rest period.
- Endurance testing at 80% peak exertion to assess baseline measures. (2 hours following maximal exercise testing)
- Adverse event monitoring

Visit 1 is anticipated to take 5-6 hours to complete. At the end of Visit 1, participants will be randomized to one of the two treatment sequences:

1. Treprostinil (Visit 2): placebo (Visit 3) or
2. Placebo (Visit 2): treprostinil (Visit 3).

### Visit 2 (Visit 2 will occur 1-2 weeks (+/- 3 days) after Visit 1)

- Insertion of venous cannula will be placed early in the visit to be used for taking venous pressure during the exercise testing.
- Vital signs (heart rate, blood pressure, oxygen saturation, height and weight)
- Blood drawn for metabolic panel (CMP), GGT, CBC (Drawn once at visit 2 or visit 3)
- Review of Concomitant Medications
- Urine pregnancy testing
- Resting ECG
- First dose of treprostinil OR placebo, as determined by the randomization following Visit 1.
- Participant blood pressure will be monitored for  $\frac{1}{2}$  hour (immediately, 15 min, and 30 min.) following the initial dose of treprostinil or placebo on a particular study day.
  - If systolic BP drops below 90 mm Hg or drops  $\geq 30$  mm Hg from the baseline, the participant's blood pressure will be monitored until return to above these thresholds. If baseline systolic blood pressure is below 90 mm Hg, then

the low threshold for additional monitoring will be 85 mm Hg for these participants.

- Study staff monitoring the blood pressure will consult with the PI or MD subI should a drop in blood pressure meeting these thresholds occur. Patient will continue with the investigation at the discretion of the PI or MD subI.
- Shear Wave Elastography (for liver stiffness)
- Vascular function assessment (Pulse Wave Velocity [PWV] and brachial Flow Mediated Dilation [FMD], already in use in this institution (described below).
- If the participant tolerated the 1st dose of treprostinil or placebo, (i.e no clinically significant drop in blood pressure or unexpected AEs deemed by the PI or MD subI to be related to study drug that would preclude the patient from continued participation) they will receive a 2nd dose of their assigned treatment (at least 2 hours after the first dose).
- If the patient did not experience a significant drop in blood pressure (as defined previously) following the 1st dose, then no further blood pressure monitoring will be required prior to the exercise test.
- If the participant experienced a drop in blood pressure (as defined previously) following the 1st dose, then blood pressure will be monitored for ½ hour (immediately, 15 min, and 30 min.) following the 2nd dose of treprostinil or placebo.
  - If systolic BP drops below 90 mm Hg or drops  $\geq$  30 mm Hg from the baseline for visit 2/visit 3, the participant's blood pressure will be monitored until return to above these thresholds.
  - Study staff monitoring the blood pressure will consult with the PI or MD subI should a drop in blood pressure meeting these thresholds occur. Patient will continue with the investigation at the discretion of the PI or MD subI.
- Venous pressure manometer set-up (including calibration) will then be conducted prior to commencing exercise testing during which the venous pressures will be measured continuously during the exercise test.
- Maximal exercise testing/Ramp protocol (including spirometry).
- Immediately following exercise, a shear wave liver elastography will be repeated
- Post recovery, vascular function assessment (FMD and PWV) will be repeated.
- Light meal followed by a break for complete exercise recovery
- If the participant tolerated the prior dose of treprostinil or placebo, (i.e no clinically significant AEs deemed by the PI or MD subI to be related to study drug that would preclude the patient from continued participation) they will receive a 3rd dose of their assigned treatment.

- If the patient did not experience a significant drop in blood pressure (as defined previously) following the prior dose, then no further blood pressure monitoring will be required prior to the exercise test.
- If the participant experienced a drop in blood pressure following the previous dose, then blood pressure will be monitored for  $\frac{1}{2}$  hour (immediately, 15 min, and 30 min.) following the 3rd dose of treprostinil or placebo.
  - If systolic BP drops below the thresholds described previously, the participant's blood pressure will be monitored until return to above these thresholds.
  - Study staff monitoring the blood pressure will consult with the PI or MD subI should a drop in blood pressure meeting these thresholds occur. Patient will continue with the investigation at the discretion of the PI or MD subI.
- Endurance exercise test at 80% peak exertion to occur 2 hours after the maximal exercise testing. This is expected to last about 4-7minutes.
  - Venous pressures will be measured during the exercise test as described herein (see Venous Cannulation).
- The participants will be observed for 60 minutes following medication administration.
- Adverse event monitoring

The visit is anticipated to take 5-6 hours.

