### **Visit 3 (Visit 3 will occur 1-2 weeks (+/- 3 days) after Visit 2.)**

- Study participants will be asked to repeat the study protocol described under Visit 2, and at that time, they will be crossed over to either active drug treatment or placebo, depending on their assigned treatment sequence.

Study staff will contact the participant approximately 2 weeks after visit 3 to assess for adverse events.

Table 1 presents the schedule of procedures for this study.

Table 1.

	Visit 1	Visit 2 and Visit 3						
		Prior to Dose 1	Dose 1	Immediately After Dose 1	Dose 2	Immediately After Dose 2	10 minutes after Maximal Exercise Test	Dose 3
Elapsed Time								
Procedures:								
Informed consent	X							
Demographics and medical history	X	X d						
Concomitant Medication Review	X	X						
Vital signs	X	X		X f		X f		X f
Resting ECG		X						
Urine pregnancy	X	X						
Randomization	X							
Administer Drug			X		X			X
Venous Pressure a						X		X
Spirometry	X c					X c		
Vascular Function (FMD/PWV)				X			X e	
Shear Wave Elastography				X			X (immediate post max exerc test)	
Maximal Exercise Ramp Test	X e					X		
Venous Structure and Function	X							
Exercise Endurance Test	X							X
Complete Metabolic Panel b , Once only, at visit 2 or 3		X						
CBC, GGT Once only at visit 2 or 3		X						
Adverse Event Monitoring	X	X	X	X	X	X	X	X

a. Venous pressure will be measured from before exercise test, every 1 minute during exercise, until 5 minutes after exercise. Cannula for venous pressure may be placed early in the day to facilitate scheduling.

b. Complete metabolic panel will include: sodium, potassium, chloride, carbon dioxide, BUN, creatinine, calcium, glucose, albumin, total protein, AST, ALT, ALP, and total bilirubin.

c Spirometry will occur prior to maximal exercise test.

[figure not shown]
d Prior to exercise testing, if medical history or adverse event questioning reveals intercurrent chest infection, wheezing, or other respiratory condition, study staff will consult with PI or designee to determine if exercise testing should proceed.

e Patients will be given a light meal during visit 1 and after the 2nd vascular test is completed at visits 2 and 3.

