## Medication Administration:

Inhaled treprostinil will be administered using the Tyvaso® inhalation system. A dose of 18mcg (3 breaths) or placebo (3 breaths) will be administered prior to the vascular function assessment (this will serve as a test dose to assess adverse effects), prior to the maximal exercise test (at minimum, 2 hours post initial dose) and then again prior to the endurance exercise test.

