## **10.2. Potential Risks**

Risks associated with this study include risks associated with placement of a venous cannula such as discomfort related to placement of the cannula, bleeding, infection. Risks associated with use of a single inhalation of treprostinil include cough, headache, nausea, dizziness, flushing, epistaxis, hemoptysis, wheezing, throat irritation and

pharyngolaryngeal/chest pain (Tyvaso Package Insert and Rhodes 2013). Risks associated with exercise stress testing in this subset of patients include arrhythmia predominantly. A breach of confidentiality is another risk of participating in a research study.

Pregnancy – Pregnancy is an exclusion criteria for the study. Participants will have pregnancy testing at visit 1, visit 2, and visit 3 prior to any study procedures. Participants will also be instructed to use birth control for the duration of the study. Acceptable methods of birth control will be discussed with the patient by the PI or designee.

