#### **11.2.3. Expectedness**

All adverse events will be classified for expectedness by the Sponsor as: Expected or Unexpected. Expected events associated with the use of treprostinil include:

- Cough
- Headache
- Nausea
- Dizziness
- Flushing
- Epistaxis
- Hemoptysis
- Wheezing throat irritation
- Pharyngolaryngeal/chest pain
- Other expected events include those associated with vascular testing, shear wave elastography, and exercise testing as determined by the PI or attending physician.

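### The rule for giving Dose 2 disregards related adverse events that are expected, so a clinically significant expected event does not fail the test dose, although the same event would block Dose 3

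*Combined protocol and SAP*

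**What the plan says.** Each treatment visit has three doses of 18 mcg or placebo. Section 6, Medication Administration, says of the first that "this will serve as a test dose to assess adverse effects"; section 7, Proposed Dose, repeats this purpose.

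Section 6, Visit 2, sets the condition for Dose 2. Dose 1 counts as tolerated if there was "no clinically significant drop in blood pressure or unexpected AEs deemed by the PI or MD subI to be related to study drug", with a closing clause that limits the events to those that would rule out further participation. If the condition is met, "they will receive a 2nd dose of their assigned treatment (at least 2 hours after the first dose". The maximal ramp test follows Dose 2.

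The condition for Dose 3, later in the same visit description, is "no clinically significant AEs deemed by the PI or MD subI to be related to study drug that would preclude the patient from continued participation". It does not contain the word *unexpected*. Visit 3 repeats the Visit 2 procedures, so both rules apply at both treatment visits.

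Section 11.2.3 opens its list with "Expected events associated with the use of treprostinil include". Section 10.2 gives the drug risks as "cough, headache, nausea, dizziness, flushing, epistaxis, hemoptysis, wheezing, throat irritation" and pharyngolaryngeal or chest pain.

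Footnote d to Table 1 covers chest infection, wheezing and other respiratory conditions found before exercise. In those cases "study staff will consult with PI or designee to determine if exercise testing should proceed".

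**The concern.** A test dose should show whether a participant reacts badly to the drug before more is given. The reactions most likely to be seen are the known ones. If known reactions are excluded from the adverse-event part of the pass rule, that part can respond only to effects nobody anticipated. Apart from a blood pressure drop, the rule would then ignore the effects that the test dose is best placed to detect.

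At stake is a second inhaled dose, ahead of a maximal exercise test, in an adult with a single-ventricle circulation who has just had a clinically significant related event. Staff would also be applying two different adverse-event standards on the same day, with the looser one at the test dose.

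**Working it through.** The plan gives no figure to reproduce, and no power or alpha calculation applies. The check compares the texts, with two short counts.

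**Step 1. Are any named drug risks unexpected?** The risks in section 10.2 are set against the list in section 11.2.3.

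| Risk named in 10.2 | On the expected list in 11.2.3? |
|---|---|
| Cough | Yes |
| Headache | Yes |
| Nausea | Yes |
| Dizziness | Yes |
| Flushing | Yes |
| Epistaxis | Yes |
| Hemoptysis | Yes |
| Wheezing | Yes (shares a bullet with throat irritation) |
| Throat irritation | Yes (shares a bullet with wheezing) |
| Pharyngolaryngeal/chest pain | Yes |

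The result is 10 of 10, with 0 left as unexpected. Section 11.2.3 sets no severity limit, and nothing there turns an expected event into an unexpected one when it is worse than usual.

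**Step 2. What must be true for an event to block each dose?**

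| Condition | Dose 2 | Dose 3 |
|---|---|---|
| Judged related to study drug by the PI or physician sub-investigator | Required | Required |
| Judged to rule out continuing | Required | Required |
| Unexpected | Required | Not required |
| Clinically significant | Stated for the blood pressure drop; may also carry over to the events | Required |
| Separate blood pressure criterion in the definition of tolerated | Yes | No |

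Reading *clinically significant* as covering both nouns in the Dose 2 rule changes nothing here, because the event must still be unexpected.

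**Step 3. Apply both rules to one event.** Take related hemoptysis that is clinically significant, is judged to rule out continuing, and comes without a blood pressure drop.

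- After Dose 1: it is on the expected list, so the adverse-event part of the rule is not triggered. There is no blood pressure drop, so that part is not triggered either. Dose 1 counts as tolerated, and the written consequence is that Dose 2 is given.
- After Dose 2: it meets every condition in the Dose 3 rule, so Dose 3 is withheld.

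The same comparison gives the same result for chest pain, wheezing, and dizziness without a blood pressure drop.

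**Step 4. Exposure at issue.** The extra amount is one dose of 18 mcg at the active visit. The cumulative dose after Dose 2 is 2 × 18 = 36 mcg, out of a planned 3 × 18 = 54 mcg.

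**Step 5. What else could stop Dose 2?** The written discretion to continue in section 6, Visit 2, and in the Blood Pressure Monitoring table is tied to blood pressure drops that reach the thresholds. Footnote d reaches wheezing by name and hemoptysis arguably. Its stated decision is about exercise, not dosing, and it does not reach chest pain or dizziness as such. If exercise were cancelled before Dose 2, that dose would probably lapse, because Medication Administration ties it to the ramp test.

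**The case against.** The strongest reply is that *unexpected* in a bedside rule need not mean absent from the list in section 11.2.3. That list sits among the safety classification and reporting provisions, and the Dose 2 rule does not cite it. Section 11.2.3 assigns expectedness to the sponsor, whereas section 11.1 assigns it to the PI, and the Dose 2 decision belongs to the PI or a physician sub-investigator. The word could carry its everyday sense. The near-identical closing clauses of the two rules suggest one intended test, loosely drafted. This stands as a caution: the literal reading is plausible but not the only one. It does not remove the problem, because expectedness is a defined classification in this protocol and staff may fairly apply it. If the word was meant loosely, replacing it loses nothing.

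The second reply is clinical judgment. The Dose 2 rule itself asks a physician whether the event rules out continuing, and a physician who thinks so would be unlikely to give more drug. Exclusion criterion 5 in section 5.2 also makes exercise testing depend on the PI's judgment, although it is an eligibility criterion and not a same-day stopping rule. Footnote d forces a consultation for respiratory events, and Table 1 schedules adverse event monitoring throughout. All of this reduces the practical risk. But a physician who withholds Dose 2 for an expected event would be departing from the definition as literally read.

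A reader might go further and infer that a participant with hemoptysis, wheezing or chest pain will certainly be redosed and sent to maximal exercise. The documents do not support that, given the judgment clause and footnote d. Nor do the two rules contradict each other: they govern different doses at different times, so nobody has to obey both at once. They are inconsistent.

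**Conclusion.** The point holds as an inconsistency in the dosing rules with a modest safety consequence. Read with section 11.2.3, the adverse-event part of the Dose 2 rule cannot be triggered by any of the 10 drug risks that the protocol names, and the Dose 3 rule has no such limit. The exposure at issue is one further 18 mcg dose at the active visit, before the ramp test. The remaining risk lies mainly in non-respiratory events, such as chest pain or dizziness without a blood pressure drop, since respiratory events at least prompt a consultation.

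The conclusion assumes that *unexpected* is read by the protocol's own list. The documents give no event rate, so the number of participants affected cannot be estimated. An assumed event rate would in any case count people with an event, not people wrongly redosed. The visit diagrams were not readable in the text available for this review. They might show an additional dosing check, but they would not remove the difference between the two written rules.

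It looks like a drafting slip and should be corrected. It has no bearing on the sample size calculation or the significance level.

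**What to change.** In the Dose 2 bullet of section 6, Visit 2, replace *unexpected AEs* with *clinically significant AEs*, and state that this applies whether or not the event is expected. Keep the blood pressure condition and the clause giving the judgment to the PI or physician sub-investigator. Visit 3 inherits the change.

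The edit is a few words and adds no procedure. The cost is in data: a few participants may stop before Dose 2, probably more often at the active visit, and would then have no ramp or endurance result for that visit. In the crossover model of section 9.2, which includes a subject term, such a participant supplies no within-person treatment difference for those endpoints. The Dose 3 rule already accepts this kind of loss for the endurance test. The reason for each stop should be recorded so that drug-related losses can be identified in the analysis.

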f Blood pressure will be monitored for 30 minutes post study drug administration (immediately, 15 min, and 30 min).. Window for blood pressure measurements is +/- 3 minutes. If no drop in BP below threshold levels following previous study drug administration, then BP will not be monitored for subsequent doses. Threshold levels for additional monitoring are a drop in systolic pressure below 90 mm Hg (or 85 mg Hg if baseline was  $\leq$  90 mm Hg) or drop of  $\geq$  30 mm Hg from baseline.

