## Blood Pressure Monitoring

Blood Pressure will be monitored following administration of treprostinil or placebo dosing as shown below. Additional blood pressure monitoring may occur at any time during the procedure at the discretion of study staff for patient safety.

[figure not shown]

If Baseline Systolic BP is:	Threshold for additional monitoring is:	Action Taken
≥90 mg Hg	drop in systolic BP to < 90 mm Hg OR drop in systolic BP of ≥ 30 mm Hg from baseline	Monitor BP until return to baseline PI or MD subI assess if patient can continue Monitor BP at next dose: immediately, 15 min, 30 min
<90 mg Hg	drop in systolic BP to < 85 mm Hg OR drop in systolic BP of ≥ 30 mm Hg from baseline	Monitor BP until return to baseline PI or MD subI assess if patient can continue Monitor BP at next dose: immediately, 15 min, 30 min

[figure not shown]

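### The protocol gives two stop points for extended blood-pressure monitoring after a drop (return above the thresholds, or return to baseline) and two cut-offs for the 85 mm Hg exception

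*Combined protocol and SAP*

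**What the plan says.** Section 6 describes blood-pressure checks after each inhaled dose in two places.

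- **Visit 2 procedures, carried to Visit 3 by reference.** After Dose 1, if a threshold is crossed, "blood pressure will be monitored until return to above these thresholds". The Dose 2 bullet measures the drop "from the baseline for visit 2/visit 3, the participant's blood pressure will be monitored until return to above these thresholds". The Dose 3 bullet reads "If systolic BP drops below the thresholds described previously, the participant's blood pressure will be monitored until return to above these thresholds". So the stop point is return above the thresholds, stated three times.
- **Blood Pressure Monitoring table.** For a baseline of 90 mm Hg or more, the trigger is a "drop in systolic BP to < 90 mm Hg OR drop in systolic BP of ≥ 30 mm Hg from baseline". For a baseline below 90, the table uses 85 in place of 90. The action column in both rows is "Monitor BP until return to baseline".

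The 85 mm Hg exception for low baselines is stated three times. The Visit 2 text introduces it with "If baseline systolic blood pressure is below 90 mm Hg, then", and the table agrees. Footnote f to Table 1 has "or 85 mg Hg if baseline was" 90 or less. Footnote f repeats the triggers and gives no stop point.

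On whether the participant goes on with the visit, the two places agree. The table says "PI or MD subI assess if patient can continue", and the visit text also leaves this to the principal investigator or a physician sub-investigator.

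**The concern.** A safety instruction should give staff one answer, and here the required monitoring has two end points. Treprostinil dilates systemic as well as pulmonary arterial beds (section 7.1), and Doses 2 and 3 are each followed by demanding exercise, so a drop in pressure is a foreseeable event that needs a clear rule.

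Compliance also becomes hard to judge. Someone who stops once pressure is back above the threshold follows the visit text and departs from the table. Section 11.1 requires protocol violations to be reported to the IRB, and the documents do not say whether this would be one.

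The cut-off in footnote f raises a smaller question of the same kind. It concerns who triggers extended monitoring, and therefore who has pressure checked after the next dose.

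**Working it through.** The plan states no figure to reproduce. The check compares the texts and then sizes the gap by hand from the protocol's thresholds.

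**1. Can the two stop points mean the same thing?** No. The table's first column sorts participants by baseline systolic pressure, and its trigger column measures a fall from that baseline. The Dose 2 bullet ties baseline to the visit day. Baseline is therefore the participant's own pre-dose pressure, not the threshold. The table is operative text, because its section says that monitoring follows what is shown there.

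**2. How far apart are they?** Let B be baseline systolic pressure in mm Hg.

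- Low threshold L = 90 if B is 90 or more, and 85 if B is below 90 (visit text and table).
- Stop point under the visit text = max(L, B − 30).
- Stop point under the table = B.
- Gap = B − max(L, B − 30).

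| B | Visit text | Table | Gap |
|---|---|---|---|
| 85 | 85 | 85 | 0 |
| 88 | 85 | 88 | 3 |
| 89 | 85 | 89 | 4 |
| 90 | 90 | 90 | 0 |
| 95 | 90 | 95 | 5 |
| 100 | 90 | 100 | 10 |
| 110 | 90 | 110 | 20 |
| 120 | just above 90 | 120 | just under 30 |
| 130 | just above 100 | 130 | just under 30 |
| 140 | just above 110 | 140 | just under 30 |

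From 120 upward the gap is just under 30 because a fall of exactly 30 still meets the trigger.

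**3. Which rule satisfies both texts?** From B = 85 upward the gap is never negative, so monitoring to baseline also takes the participant past the threshold. Below 85 the order reverses. At B = 82, for example, the threshold rule would hold the participant until 85, which is 3 mm Hg above the pre-dose value, while the baseline rule stops at 82.

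**4. Footnote f.** Its cut-off differs from the other two only at B = 90 exactly. There, readings of 85 to 89 trigger extended monitoring under the visit text and the table but not under footnote f. Applying footnote f's threshold at B = 90 gives a gap of 90 − 85 = 5 instead of 0.

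**The case against.** The strongest reply is that nothing of consequence follows. After a drop, staff must consult a physician, who decides on continuation. Pressure is taken again after the next dose. Participants are observed for 60 minutes after medication, and staff may take extra readings at any time. A cautious team can monitor to baseline and, at baselines of 90 or more, satisfy both texts. The footnote matters at a single baseline value. Figures are also missing around the table, so something not visible might reconcile the rules.

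Much of this stands. The safeguards limit the harm, and the statement that nothing reconciles the rules must be confined to the visible text. But none of the safeguards says when required monitoring ends. Permission to take extra readings is not a stop rule, and nothing tells staff to choose the stricter text.

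Two stronger readings are tempting and are not supported.

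- **That the conflict controls when exercise starts, and so could disturb the endurance result.** Both texts leave continuation to the physician, and neither makes the ramp test wait a fixed time for the stop point. The safety endpoint in section 9.1 is defined by the fall in pressure, not by recovery.
- **That Dose 2 has its own threshold, because its bullet mentions only 90 mm Hg.** The visit text sets the 85 mm Hg exception for participants with low baselines, not for one dose. The table is not dose-specific, and the lead-in to the Dose 2 bullet refers back to the earlier definition. Leaving a standing exception unrepeated is not a contradiction.

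**Conclusion.** The inconsistency is real, is in current operative text, and is minor. One safety action has two stop points, which differ by 0 to just under 30 mm Hg at baselines of 85 or more; the gap exceeds 10 mm Hg only when baseline is above 100. The cut-off for the 85 mm Hg exception is inconsistent at a baseline of exactly 90.

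This rests on reading baseline as the participant's pre-dose systolic pressure on the visit day, and on the visible text being complete on this point. The stop-point conflict arises only after a drop. The documents give neither the frequency of drops nor the distribution of baseline pressure, so the number of affected doses cannot be estimated. Nothing here touches the primary endpoint, the sample size or the crossover analysis.

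**What to change.** State one stop rule in both places.

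- **Default:** in the three visit-text bullets (Doses 1, 2 and 3), replace return above the thresholds with the table's rule, "Monitor BP until return to baseline". At baselines of 90 or more this satisfies both current texts, and it is the safer rule.
- **Alternative:** if the investigator judges return above the thresholds clinically sufficient, change both rows of the table to match. That should be a deliberate clinical decision. The threshold wording appearing more often is not a reason to prefer it.
- **In either case:** change the cut-off in footnote f from 90 or below to below 90 mm Hg, to agree with the visit text and the table.

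The cost is three bullets or two table cells, plus one symbol in a footnote. The default means longer monitoring after a drop; the documents give no recovery times from which to say how much longer. The alternative adds no monitoring relative to the visit text, but a participant with a baseline of 140 could then stop just above 110.
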